#### **5.3.1 Peri-Dosing AEs**

The incidence of peri-dosing events (desaturation, bradycardia, ET reflux, hypotension, gagging/regurgitation/vomiting) will be summarized.

### **5.3.2 AEs Related to Surfactant Administration (AEs of Special Interest)**

Individual air leaks (eg, pneumothorax, pulmonary interstitial emphysema, pneumo-mediastinum, pneumopericardium, and subcutaneous emphysema) will be identified by medical review of all AEs and summarized by treatment group.

Occurrences of apnea, bradycardia, and desaturation after the peri-dosing period will be summarized by treatment group.

### **5.3.3 Other TEAEs**

TEAEs, other than those listed above, will be summarized by treatment group by the MedDRA preferred term and SOC for all TEAEs, regardless of relationship to study drug, and for TEAEs at least remotely related. If a TEAE occurs multiple times for the same subject within the same term or body system, only the most severe occurrence for that term or body system will be counted.

In addition, all TEAEs will be summarized by severity (mild, moderate, severe), relationship to the study drug (unrelated, unlikely related, possibly related, related), whether or not the TEAE was device related, and, if sufficient number of subjects warrant, by gender, race, and ethnic origin.

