2.4 Risk/Benefit Assessment

2.4.1 Known Potential Risks

Risks for this study must be considered within the context of treating adults with COVID-19, which carries with it substantial risk of morbidity and mortality. Intratracheal instillation of surfactant into the lung requires endotracheal intubation, often with concomitant positive pressure MV. However, patients in this trial will have been intubated to treat their underlying condition. MV is associated with morbidities such as ventilator-associated lung injury and volutrauma/barotrauma resulting in air leak syndromes such as pneumothorax and/or pulmonary interstitial emphysema (PIE). Surfactant instilled intratracheally has been associated with peridosing events such as transient hypoxemia, bradycardia, and hypotension. These are usually not severe, are transient, and typically resolve within 30 minutes.

Studies in adults with ARDS administered lucinactant using bronchopulmonary surfactant lavage of each segment of the lungs to attempt to remove alveolar debris and effectively deposit functional surfactant. Safety results show that this procedure was generally safe and well tolerated; however, this procedure was more invasive than other delivery methods and required more time and skill to complete dosing and may have contributed to the increased treatment-emergent AE in the lucinactant-treated subjects. A total of 44 of 110 lucinactant patients (40%) and 14 of 42 standard of care patients (33%) experienced an SAE. A total of 15 of 88 lucinactant patients (17%) in KL4-ARDS-04 had an SAE that was considered to be related to study treatment (patients receiving

standard of care had all AEs and SAEs defined as not study-treatment related). A total of 28 deaths were observed in the ARDS studies. In the KL4-ARDS-04 Study, all-cause mortality at the end of Day 28 was numerically, but not statistically significantly, higher in lucinactant Group B.2 (24%) compared with lucinactant Group B.1 and SOC (14% in each).

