### **5.3.4 Serious Adverse Events**

An AE or suspected adverse reaction is considered “serious” if, in the view of either the investigator or sponsor, it results in any of the following outcomes: death, a life-threatening adverse event, inpatient hospitalization or prolongation of existing hospitalization, a persistent or significant incapacity or substantial disruption of the ability to conduct normal life functions, or a congenital anomaly/birth defect. Important medical events that may not result in death, be life-threatening, or require hospitalization may be considered serious when, based upon appropriate medical judgment, they may jeopardize the participant and may require medical or surgical intervention to prevent one of the outcomes listed in this definition. Examples of such medical events include allergic bronchospasm requiring intensive treatment in an emergency room or at home, blood dyscrasias or convulsions that do not result in inpatient hospitalization.

All SAEs will be listed and summarized by treatment group using frequency counts and percentages. If the same SAE occurs multiple times for the same subject, the most severe occurrence will be counted. SAEs, including multiple occurrences, will also be listed, to include severity, relationship to the study drug, gender, race, and ethnic origin.

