- 4.9.1 Efficacy Analysis – Plateau Pressure and Peak Inspiratory Pressure (PIP) through 24 Hours – Modified Intent-to-Treat Population
- 4.9.2 Efficacy Analysis – Plateau Pressure and Peak Inspiratory Pressure (PIP) through 24 Hours – Intent-to-Treat Population
- 4.10.1 Efficacy Analysis – Ventilation Index (VI) through 24 Hours – Modified Intent-to-Treat Population
- 4.10.2 Efficacy Analysis – Ventilation Index (VI) through 24 Hours – Intent-to-Treat Population
- 4.11.1 Efficacy Analysis – Lung Compliance (Dynamic) through 24 Hours – Modified Intent-to-Treat Population
- 4.11.2 Efficacy Analysis – Lung Compliance (Dynamic) through 24 Hours – Intent-to-Treat Population
- 4.12.1 Efficacy Analysis – Daily Lung Compliance (Static) on Ventilator – Modified Intent-to-Treat Population
- 4.12.2 Efficacy Analysis – Daily Lung Compliance (Static) on Ventilator – Intent-to-Treat Population
- 4.13.1 Efficacy Analysis – Ventilator Free Days – Modified Intent-to-Treat Population
- 4.13.2 Efficacy Analysis – Ventilator Free Days – Intent-to-Treat Population
- 4.14.1 Efficacy Analysis – Days in the Intensive Care Unit (ICU) – Modified Intent-to-Treat Population
- 4.14.2 Efficacy Analysis – Days in the Intensive Care Unit (ICU) – Intent-to-Treat Population
- 4.15.1 Efficacy Analysis – Days in the Hospital – Modified Intent-to-Treat Population
- 4.15.2 Efficacy Analysis – Days in the Hospital – Intent-to-Treat Population
- 4.16.1 Efficacy Analysis – Incidence of All-Cause Mortality – Modified Intent-to-Treat Population
- 4.16.2 Efficacy Analysis – Incidence of All-Cause Mortality – Intent-to-Treat Population
- 4.17.1 Efficacy Analysis – Organ Failure Free Days – Modified Intent-to-Treat Population
- 4.17.2 Efficacy Analysis – Organ Failure Free Days – Intent-to-Treat Population
- 5.1.1 Peri-Dosing Adverse Events – Initial Dose – Safety Population
- 5.1.2 Peri-Dosing Adverse Events – Repeat Doses – Safety Population
- 5.2 Air Leaks – Safety Population
- 5.3.1 Treatment-Emergent Adverse Events by System Organ Class and Preferred Term – Safety Population
- 5.3.2 Treatment-Emergent Adverse Events by System Organ Class and Preferred Term by Severity – Safety Population
- 5.3.3 Treatment-Emergent Adverse Events by System Organ Class and Preferred Term by Relationship to Study Treatment – Safety Population
- 5.3.4 Treatment-Emergent Adverse Events by System Organ Class and Preferred Term by Severity and Relationship to Study Treatment – Safety Population

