- 5.3.5 Treatment-Emergent Adverse Events in Descending Order of Frequency – Safety Population
- 5.4.1 Serious Adverse Events by System Organ Class and Preferred Term – Safety Population
- 5.4.2 Serious Adverse Events by System Organ Class and Preferred Term by Severity – Safety Population
- 5.4.3 Serious Adverse Events by System Organ Class and Preferred Term by Relationship to Study Treatment – Safety Population
- 5.4.4 Serious Adverse Events by Preferred Term in Descending Order of Frequency – Safety Population
- 5.5 All-Cause Mortality – Safety Population
- 6.1.1 Clinical Assessments – Vital Signs – Body Temperature – Observed Values and Change from Baseline – Safety Population
- 6.1.2 Clinical Assessments – Vital Signs – Blood Pressure – Observed Values and Change from Baseline – Safety Population
- 6.1.3 Clinical Assessments – Vital Signs – Heart Rate – Observed Values and Change from Baseline – Safety Population
- 6.1.4 Clinical Assessments – Vital Signs – Respiratory Rate – Observed Values and Change from Baseline – Safety Population
- 6.2 Clinical Assessments – Physical Examination – Safety Population
- 6.3 Clinical Assessments – Respiratory Support – Mechanical Ventilation – Safety Population
- 6.4 30-Day Follow-Up – General Health Assessments – Safety Population

Listing      Title

- 1.1 Protocol Violations/Deviations
- 2.1 All-Cause Mortality
- 2.2 Serious Adverse Events
- 2.3 Treatment-Emergent Adverse Events
- 3.1 Pre-Study/Concomitant Medications
- 4.1 Description of Early Termination of Treatment
- 5.1 Reporting of Pregnancy

Figure      Title

- 1.1 Change from Baseline in Oxygenation Index (OI)
- 1.2 Change from Baseline in FiO2
- 1.3 Change from Baseline in PaO2
- 1.4 Change from Baseline in SpO2
- 1.5 Change from Baseline in PaCO2

- 2.1 Change from Baseline in ETCO2
- 2.6.1 Change from Baseline of P/F Ratios
- 2.6.2 Change from Baseline of S/F Ratios
- 2.7.1 Change from Baseline in Plateau Pressure
- 2.7.2 Change from Baseline in PIP
- 2.7.3 Change from Baseline in PEEP
- 2.8 Change from baseline in Ventilation Index (VI)

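### The SAP's only rule for repeated adverse events selects by severity; the relationship summaries have no rule of their own, so related-event rates can be understated

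*SAP*

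**What the plan says.** **Counting rules.** For a TEAE that recurs in the same subject within a term or body system, SAP 5.3.3 states that "only the most severe occurrence for that term or body system will be counted". SAP 5.3.4 does the same for serious events: "If the same SAE occurs multiple times for the same subject, the most severe occurrence will be counted". No other rule for repeated events appears in the SAP.

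**Planned relationship summaries.**
- The paragraph of SAP 5.3.3 that holds the counting rule begins: "TEAEs, other than those listed above, will be summarized by treatment group by the MedDRA preferred term and SOC for all TEAEs". It plans these summaries "regardless of relationship to study drug, and for TEAEs at least remotely related", so a related-only summary is intended.
- The next paragraph adds: "In addition, all TEAEs will be summarized by severity (mild, moderate, severe), relationship to the study drug". It contains no counting rule.
- SAP Section 10 lists Table 5.3.3, "Treatment-Emergent Adverse Events by System Organ Class and Preferred Term by Relationship to Study Treatment", Table 5.3.4, which crosses severity with relationship, and Table 5.4.3, "Serious Adverse Events by System Organ Class and Preferred Term by Relationship to Study Treatment".

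**What stands outside the rule.** SAP 5.3.1 gives peri-dosing events their own incidence summary (Table 5.1.1 for the initial dose, Table 5.1.2 for repeat doses). SAP 5.3.2 separately summarizes air leaks, and apnea, bradycardia and desaturation that occur after the peri-dosing period. SAP 5.3.4 lists every occurrence of an SAE with its severity and relationship, and Listing 2.3 covers TEAEs.

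**The concern.** Selecting one record per subject by severity suits a severity table. It does not suit a table asking how many subjects had an event attributed to the drug, because severity and attribution are different properties of an event. The record kept for its severity may carry a different attribution from the one discarded.

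The pattern that would cause a loss is plausible here. Protocol 2.4.1 says of the transient hypoxemia, bradycardia and hypotension seen with instilled surfactant: "These are usually not severe, are transient, and typically resolve within 30 minutes". Adverse events are then collected through Day 30 (Protocol 8.4.5) in ventilated, critically ill patients, in whom the same term may recur in a worse form from the underlying disease.

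Safety and tolerability is a primary endpoint (SAP 1.2.2). With no comparison group (Protocol 9.1), investigator attribution carries part of the safety interpretation. The sponsor uses such rates itself: Protocol 2.4.1 reports that 15 of 88 lucinactant patients (17%) in an earlier ARDS study had a treatment-related SAE. In an open-label trial, the choice of counting rule should be written down before the data are tabulated.

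**Working it through.** The plan states no adverse-event rate, so there is no figure to reproduce. The check applies the possible counting rules to one case, then works out direction and size.

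**1. One constructed subject.** Mild hypotension on Day 1, judged related; severe hypotension on Day 5, judged unrelated.

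| Order of steps | Record kept | Counted as related? |
|---|---|---|
| Most severe first, then read its relationship | Day 5, severe, unrelated | No |
| Select related events, then take the most severe | Day 1, mild, related | Yes |
| Take the most closely related occurrence | Day 1, mild, related | Yes |

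The SAP does not say which order applies. In body-system rows for TEAEs, the displacing event need not share the preferred term, because the rule in SAP 5.3.3 also operates within a body system.

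**2. Direction.** Let S be the subjects with at least one related occurrence of a term, and T those whose most severe occurrence is related. Every member of T is in S, so T cannot outnumber S. Severity-first counting reports T where S is wanted. The error can only lower a related rate.

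**3. Size per displaced subject.** The sample size is 20 in SAP 2.2.3 and up to 30 in Protocol 9.2.
- N = 20: 1/20 = 5.0 percentage points.
- N = 30: 1/30 = 3.3 percentage points.

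**4. Frequency, by assumption only.** Let r be the share of subjects with a related event in a term, and q the share of those who also have a worse unrelated event in that term. Neither value is in the documents. The expected understatement is r × q, and the chance of at least one displaced subject is 1 − (1 − rq)^N.
- r = 10%, q = 10%: 0.10 × 0.10 = 1 point.
- r = 20%, q = 25%: 0.20 × 0.25 = 5 points. The chance of at least one displaced subject is 1 − 0.95^20 = 64% at N = 20, and 1 − 0.95^30 = 79% at N = 30.
- r = 50%, q = 50%: 0.50 × 0.50 = 25 points.

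The assumed range therefore gives 1 to 25 points under severity-first counting. If related events are selected first, the understatement is 0 whatever r and q are.

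**The case against.** A reader might infer that the SAP orders the severity rule in the relationship tables, that mild dosing events therefore vanish, and that related rates will be understated. The documents do not support that reading, for four reasons.

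- **The reach of the rule is inferred.** The TEAE rule sits in the paragraph on preferred-term and body-system summaries. The relationship summaries follow in a separate paragraph that is silent on counting. This stands. The fault is a missing rule beside a stated one that does not suit, and if the stated rule does not reach these tables they have none.
- **Dosing events are tabulated elsewhere.** Peri-dosing desaturation, bradycardia, reflux, hypotension and gagging, regurgitation or vomiting appear in Tables 5.1.1 and 5.1.2, and later apnea, bradycardia and desaturation are summarized separately. This stands for incidence: the events stay visible. But those tables are not said to show relationship, the relationship summary covers all TEAEs, and later hypotension is not on the separate list in SAP 5.3.2.
- **The related-only summary may already be right.** Its natural reading is that related events are selected first, in which case nothing is lost. This is fair, but the SAP leaves the order unstated.
- **SAE records can be recovered.** Displacement needs two occurrences of the same SAE in one subject, the worse one unrelated, which should be uncommon. The listing keeps both. This stands, although no related rate is planned from the listing.

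It is also true that no hypothesis or stopping boundary in the plan depends on a related-event rate.

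**Conclusion.** The point holds as a gap in specification that should be closed. The only repeat-event rule is severity-based. For SAEs it sits in the section that governs Table 5.4.3; for TEAEs it directly follows the planned related-only summary. A programmer who applies it as written can lose related events from the relationship tables.

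That related rates *can* be understated, and cannot be overstated, follows from the rule alone. That they *will* be understated, or by how much overall, does not: it depends on the order of steps chosen and on event overlap, for which the documents give no figures. The firm size is 5.0 points per displaced subject at N = 20, or 3.3 at N = 30. The 1 to 25 point range is illustrative. The exposure is greatest for TEAE relationship tables and least for SAEs.

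**What to change.** In SAP 5.3.3 and 5.3.4:

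1. Limit the most-severe rule to the severity tables.
2. State that relationship tables (Tables 5.3.3 and 5.4.3) count, for each subject and term, the most closely related occurrence, and do the same within body-system rows.
3. State that any related-only summary selects related events before a severity rule is applied. Say which categories of the SAP's four-level relationship scale qualify, since the wording used for that summary is not one of them.
4. In the severity-by-relationship table (Table 5.3.4), take the most severe occurrence separately among related or possibly related events and among the rest.

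The cost is a few sentences and a changed sort order in three tables. No new data are needed: Protocol 8.4.5 already requires severity and relationship for each adverse event.

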### **5.3.4 Serious Adverse Events**

An AE or suspected adverse reaction is considered “serious” if, in the view of either the investigator or sponsor, it results in any of the following outcomes: death, a life-threatening adverse event, inpatient hospitalization or prolongation of existing hospitalization, a persistent or significant incapacity or substantial disruption of the ability to conduct normal life functions, or a congenital anomaly/birth defect. Important medical events that may not result in death, be life-threatening, or require hospitalization may be considered serious when, based upon appropriate medical judgment, they may jeopardize the participant and may require medical or surgical intervention to prevent one of the outcomes listed in this definition. Examples of such medical events include allergic bronchospasm requiring intensive treatment in an emergency room or at home, blood dyscrasias or convulsions that do not result in inpatient hospitalization.

All SAEs will be listed and summarized by treatment group using frequency counts and percentages. If the same SAE occurs multiple times for the same subject, the most severe occurrence will be counted. SAEs, including multiple occurrences, will also be listed, to include severity, relationship to the study drug, gender, race, and ethnic origin.

### **5.3.5 Deaths**

All-cause mortality and deaths due to RDS during the study will be summarized by treatment group using frequency counts and percentages. Deaths by subject will also be listed and will include primary cause, date and time of death, gender, race, and ethnic origin.

## **5.4 Clinical Assessments of Safety**

### **5.4.1 Vital Signs**

Vital signs, including body temperature, blood pressure, and heart rate, will be measured every 12 ( $\pm 1.0$ ) hours until Day 5 and at Day 30. Systolic and diastolic blood pressure should be measured using either an arterial line or a manual sphygmomanometer with the patient in a supine or semi-supine position. Weight will be measured at baseline and at Day 30.

Clinically significant vital signs will also be recorded as AEs.

### **5.4.2 Physical Examination**

For each body system evaluated at screening and at the final physical examination, frequency counts and percentages of normal and abnormal results will be summarized by treatment group. In addition, a shift table to describe the changes in normal/abnormal results between screening and the final visit will be presented. Any new abnormal physical examination findings must be documented as AEs.

### **5.4.3 Respiratory Support and Supplemental Oxygen**

The respiratory support includes mechanical ventilation and extracorporeal membrane oxygenation (ECMO). Information on respiratory support parameters will be captured from screening through Day 30 or discharge, whichever occurs first. For each intubation and change in respiratory support, date and time, the type of respiratory support and mode, the reason for each intubation and change of respiratory support will be documented.

Lung compliance should be recorded every 12 ( $\pm 1.0$ ) hours through Day 5. The plateau pressure and peak inspiratory pressure (PIP) will be measured every 12 ( $\pm 1.0$ ) hours through Day 5. The ventilation index will be calculated.

The number of subjects requiring respiratory support in the delivery room, including sustained inflation, will be summarized using frequency and percent.

## **5.5 Follow-Up**

The follow-up period is from Day 6 to Day 30. The assessments conducted at the final visit (Day 30), including vital signs, ABG (PaO2, PaCO2, pH), FiO2, SpO2, Paw, EtCO2, Respiratory support parameters, AEs/SAEs, and Concomitant medications.

## **6 INTERIM ANALYSES AND DATA MONITORING**

### **6.1 Data Monitoring Committee**

The DMC, made up of at least 3 experts in the field of infectious diseases, will evaluate the degree of risk involved in study subject participation within each treatment group and to determine if study continuation in accordance with the current protocol holds the potential to institute any undue harm or threat to the safety and welfare of study subjects.

During the treatment and post-dosing phases, the chair of the DMC will receive regular reports on SAEs and DMC members will be periodically updated on the program and trial status. An ad hoc meeting of the DMC will occur if the chair deems it necessary to address safety in the study. The DMC may recommend that study enrollment be suspended if safety concerns are identified or suspected.

The DMC will meet after every 6 subjects have been enrolled and dosed. The DMC will continue to meet after every 6 enrollments and these reviews will continue until enrollment and dosing is complete.

The DMC review may consist of the evaluation of (1) demographics and baseline, (2) all AEs, especially peri-dosing AEs and AEs of special interest, (3) case reviews of subjects with reported SAEs, (4) summary tables of all safety endpoints, and (5) any other available relevant data.

Following a meeting, the DMC will provide timely recommendations to the Windtree study team. Recommendations may consist of, but not be limited to the following:

- Continue the study as planned
- Suspend study enrollment, pending additional information
- Close study enrollment

An independent statistician, not a member of the committee, will be responsible for the statistical analysis of the data.

### **6.2 Interim Analyses/DMC Meetings**

No interim analyses are planned, other than the safety assessments performed by the DMC.

### **6.3 Data Monitoring**

Clinical data (including AEs, concomitant medications, and expected adverse reactions data) will be entered into a 21 CFR Part 11-compliant data capture system. The data system includes password protection and internal quality checks, such as automatic range checks, to identify data that appear inconsistent, incomplete, or inaccurate.

Members of Windtree's Data Management department are responsible for data processing, in accordance with procedural documentation and a study specific Data Management Plan (DMP). Windtree's Data Management will also provide eCRF Completion Guidelines; extra training will be provided to the study sites when necessary.

Clinical data will be entered directly from the source documents. After data have been entered into the study database, a system of computerized data validation checks will be implemented and applied to the database on a regular basis. Corrections for an existing eCRF record will automatically be recorded by the eCRF system (audit trail capturing the time, date, and the identification of the user who entered or updated eCRF data). Recorded corrections by the eCRF will create an electronic audit trail of study documentation.

Database lock will occur once all quality assurance procedures have been completed; this will include but not be limited to the following: (1) all site-based study data have been entered into the eCRF, (2) all entered data have been reconciled and reviewed by Windtree or designee, and (3) all data related queries have been rendered and resolved.

All procedures for the handling and analysis of data will be conducted using good computing practices meeting FDA guidelines for the handling and analysis of data for clinical trials.

